6.2.2 Annual Severity Increment Score (ASIS)

The Annual Severity Increment Score (ASIS) [Cortina-Borja et al, 2018] is a metric that measures the annual increment in clinical severity for individual NPC patients. The ASIS score is based on the assessments performed in the NPC-CSS assessment; no additional tests are required. The ASIS score is obtained by dividing the total NPC-CSS severity score of a patient by the age of the patient, providing a measure of the rate of disease progression in individual patients.

Cortina-Borja et al (2018) demonstrated in 38 patients from two independent international clinical cohorts that the ASIS was stable over several years. They also applied the ASIS score to quantify the slowing of the rate of disease progression in 10 NPC patients receiving long-term treatment with Acetyl-DL-Leucine. The study demonstrated that the ASIS is a reliable predictor of progression of clinical severity and a valuable tool to quantify the effect of an experimental therapy for NPC disease progression.

The ASIS scale is included to quantify the potential effects of IB1001 as a neuroprotective/disease-modifying treatment for NPC.

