6.5.3 Baseline characteristics

The following relevant patient baseline characteristics will be listed and summarized overall (frequency and percentage) and are considered key subgroups, and will only be used for presentations of the primary endpoint in Extension phase I analyses:

- Naïve versus non-naïve, as determined at screening during the parent study
- Age (paediatric versus adult) at Visit 7
- Gender (male versus female)
- Age/weight/dosing group as applicable at Visit 7
- Selected Primary Anchor Test (9HPT-D or 8MWT) as defined during the parent study
- Patients on miglustat vs Patients not on miglustat at Visit 7
- Composite of SARA Subtests 1- 4 (Gait, Stance, Sitting, Speech): classification based on below (\leq)/above the median value at Visit 7
- Composite of modified (5 domain) NPC-CSS score: classification based on below (\leq)/above the median value at Visit 7
- ASIS: classification based on below (\leq)/above the median value at Visit 7
- Age of diagnosis: Early-infantile (<2 years), Late-infantile (2 to < 6 years), Juvenile (6 to < 15 years), Adolescent/Adult (\geq 15 years)
- Disease severity: classification based on NPC-CSS below (\leq)/ above the median score at Visit 7.

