It is important to realize that the CGI-S and CGI-C scores per visit for each patient as provided by the caregiver may be based on varying caregivers and hence additional variation is introduced. No correction for this variation can be done and a footnote will be added to the table to describe this situation.

Measurement of Disease Progression

Descriptive statistics will be provided for (15 domain) NPC-CSS total sum score, including Visit 1 of the parent study if collected. Change from baseline (Visit 9 versus Visit 7) will be presented descriptively as well. The sum of the major domains (ranging from 0-40), the sum of the modifier domains (ranging from 0-14), and each domain subscore at each visit will not be presented descriptively, and only included in listings.

The ASIS score is obtained by dividing the total NPC-CSS severity score of a patient by the age of the patient (at Visit 9), providing a measure of the rate of disease progression in individual patients. Descriptive statistics for ASIS will be provided, including the change in ASIS score from Visit 7 to Visit 9.

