in case all tests were imputed because of missing values, no SCAFI score will be determined. This contradicts the “SCAFI rating manual”.

SARA

The overall SARA score is reported as provided in the eCRF. For presentation of the subscore results, the individual results as provided in the eCRF will be used, where for the subscores finger chase, nose-finger test, fast alternating hand movements, heel-shin slide this is the average value for the two sides (left and right) as determined per eCRF.

mDRS

The mDRS composite score (only relevant for the Parent Study) is calculated as a sum of the separate subscores divided by 24. If one of the subscores is missing, the mDRS composite score is missing as well. As compared to the official questionnaire, the eCRF allows values of 0 (“normal”) for the subscores.

Modified NPC-CSS and ASIS

The modified (15 domain) NPC-CSS total score is calculated as the sum of the 8 major and the 7 modifier scores, and ranges from 0-54. This is referred to as the (15 domain) NPC-CSS sum/total score. The modified (5 domain) NPC-CSS consists of the domains for Ambulation, Cognition, Fine motor, Speech and Swallowing. The ASIS score is obtained by dividing the total (15 domain) NPC-CSS severity score of a patient by the age of the patient at Visit 9, providing a measure of the rate of disease progression in individual patients. The modified (15 domain) NPC-CSS total score, the modified (5 domain) NPC-CSS score and the ASIS score are all only relevant for the Extension Phase.

If one of the NPC-CSS subscores is missing, the total sum scores will be missing as well and so will the ASIS score.

Durations, determination of baseline values and handling of missing data will be programmed as stated in the respective analysis sections.

Laboratory

Laboratory safety data measurements that are denoted as smaller/larger than a certain value (e.g. < x.x), will be imputed with this value (e.g. x.x) for calculations of descriptive statistics. Listings will show the value as collected, and a footnote will be added to the summary tables for explanation.

Comments

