12.3 End-of-text tables and graphs

Following ICH E3 guidelines, all tables and graphs mentioned here will be presented in Section 14 of the CSR, and tables will be prepared in the order and with section number as stated.

Table/graph number	Contents of table/graph
14.1 Demographic Data Summary figures and tables	
14.1.11-14.1.13	Demographics (mITTe and SAFe)
14.1.14-14.1.15	Baseline characteristics (mITTe)
14.1.16	Disposition
14.1.17	Medical history
14.1.18	NPC specific history
14.1.19	Compliance
14.2 Efficacy Data Summary figures and Tables	
14.2.63	Frequency table, p-value, and CI on the primary endpoint (5 domain) NPC-CSS success rate (mITTe)
14.2.64	Frequency table on the primary endpoint (5 domain) NPC-CSS success rate (mITTe), according to subgroups.

14.2.65	Descriptive statistics on 5 domain NPC-CSS sum score, including change values between visits (mITTe).
14.2.66	Descriptive statistics on 5 domain NPC-CSS sum score, including change values between visits (mITTe) according to subgroups.
14.2.67	Spaghetti plot of the (5 domain) NPC-CSS sum score through time.
14.2.68	Descriptive statistics of the SARA total score at each visit, including change values between visits (mITTe)
14.2.69	Descriptive statistics of the SCAFI total score and subscores 8MW_avg, 9HPT-D_avg, 9HPT-ND_avg and PATA_avg at each visit, including change values between visits (mITTe)
14.2.70	Frequency table of the EQ-5D-5L and EQ-5D-Y health status and 5 subdomains at each visit (mITTe)
14.2.71	Descriptive statistics of the EQ-VAS for -5L and -Y combined at each visit (mITTe)
14.2.72	Descriptive statistics of the (15 domain) NPC-CSS sum score at each visit, including change from baseline (mITTe)
14.2.73	Descriptive statistics of the ASIS score at each visit, including change from baseline (mITTe), if available
14.2.74	Frequency table of the 3 CGI-S scores (treating physician, caregiver and patient) at each visit (mITTe)
14.2.75	Descriptive statistics of the 3 CGI-S scores (treating physician, caregiver and patient) at each visit (mITTe)
14.2.76	Frequency table of the 3 CGI-C scores (treating physician, caregiver, and patient) at each visit (mITTe)
14.2.77	Descriptive statistics of the 3 CGI-C scores (treating physician, caregiver, and patient) at each visit (mITTe)
14.3 Safety Data Summary figures and tables – 14.3.1 Displays of Adverse Events	
14.3.1.10	Overview adverse events
14.3.1.11	Treatment emergent adverse events

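### ASIS is divided by age at Visit 9 whichever visit the score comes from, so its Visit 7 to Visit 9 change is not a change in progression rate and leans toward worsening

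*SAP*

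**What the plan says.** Protocol Appendix 6, section 6.2.2 obtains ASIS by "dividing the total NPC-CSS severity score of a patient by the age of the patient, providing a measure of the rate of disease progression". It names no visit for the age. It reports that in earlier cohorts "the ASIS was stable over several years", and it includes the measure to quantify a possible neuroprotective or disease-modifying effect.

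The SAP ties the age to one visit, in two places. Section 6.6.3 divides the total score "by the age of the patient (at Visit 9), providing a measure of the rate of disease progression in individual patients". Section 10.1 defines ASIS by "dividing the total (15 domain) NPC-CSS severity score of a patient by the age of the patient at Visit 9".

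Three planned outputs need ASIS at other visits:

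- Section 6.6.3: "Descriptive statistics for ASIS will be provided, including the change in ASIS score from Visit 7 to Visit 9".
- Section 12.3, Table 14.2.73: "Descriptive statistics of the ASIS score at each visit, including change from baseline (mITTe), if available".
- Section 6.5.3, a baseline subgroup: "ASIS: classification based on below" or above the median at Visit 7.

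Section 10.1 also has a general age rule. Age is not collected in the extension, so any age needed for a calculation at Visit 7, 8 or 9 is to come from that visit's date and the birth date. The rule does not mention ASIS. SAP section 7, which records departures from the protocol, does not list a changed ASIS denominator.

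**The concern.** ASIS is meant as a rate: severity accumulated per year of life. If a patient keeps progressing at the earlier rate, score and age rise together and the ratio stays put. That is what the reported stability implies, and it makes zero change the natural reference for unaltered disease. The property holds only if each score is divided by the age at which it was taken.

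Dividing the Visit 7 score by the Visit 9 age removes it. The planned change would then repeat the raw NPC-CSS change, already tabulated in Table 14.2.72, on another scale. It could not show slowing relative to the patient's own past, which is why the protocol added the measure. The Visit 7 subgroup would also depend on whether and when the patient attended Visit 9.

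**Working it through.** The documents state no ASIS value, so there is no figure to reproduce. The check is algebraic.

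**Inputs from the documents.** A higher NPC-CSS score is worse (SAP 6.6.1). The 15-domain total runs from 0 to 54, which agrees with 40 for the major plus 14 for the modifier domains. Visit 7 to Visit 9 is 365 days (±14). Patients are at least 6 years old in Europe and at least 18 in the US at parent-study entry.

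**Assumptions.** The ages below and a Visit 7 score of 20 are illustrative.

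**Notation.** S7 and S9 are the 15-domain totals, A7 and A9 the ages, and d = A9 − A7 = 365/365.25 = 0.9993 years.

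1. Own-age change = S9/A9 − S7/A7.
2. SAP change = S9/A9 − S7/A9 = (S9 − S7)/A9.
3. SAP minus own-age = S7/A7 − S7/A9 = S7 × d/(A7 × A9). S9 drops out, so the excess is the same whatever happens on treatment. It is positive for any S7 above 0.
4. As a share of the Visit 7 ASIS (S7/A7), the excess is d/A9: 14.3% at age 6, 9.1% at 10, 5.3% at 18, 3.2% at 30 and 2.2% at 45.
5. The SAP change has the wrong sign whenever the score rises by more than 0 but less than (S7/A7) × d.

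Worked case, age 10 and score 20, so A9 = 10.9993. For halted disease, the own-age change is 20/10.9993 − 20/10 = 1.818 − 2.000 = −0.182, and the SAP change is 0/10.9993 = 0. For progression at the prior rate, S9 = 20 + 2 × 0.9993 = 21.9986. The own-age change is 2.000 − 2.000 = 0, and the SAP change is 1.9986/10.9993 = +0.182.

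| Age at Visit 7 (score 20) | Course to Visit 9 | Own-age change | SAP change |
|---|---|---|---|
| 6 | score unchanged | −0.476 | 0.000 |
| 6 | prior rate | 0.000 | +0.476 |
| 6 | +1 point | −0.333 | +0.143 |
| 10 | score unchanged | −0.182 | 0.000 |
| 10 | prior rate | 0.000 | +0.182 |
| 10 | +1 point | −0.091 | +0.091 |
| 18 | score unchanged | −0.058 | 0.000 |
| 18 | prior rate | 0.000 | +0.058 |
| 18 | +1 point | −0.006 | +0.053 |
| 45 | score unchanged | −0.010 | 0.000 |
| 45 | prior rate | 0.000 | +0.010 |

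At age 18 with score 20, the ±14-day visit window moves the excess only between 0.056 and 0.061.

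**Subgroup.** The SAP rule multiplies each Visit 7 ASIS by A7/A9, which is 6/6.9993 = 0.857 at age 6 and 45/45.9993 = 0.978 at age 45. The factor differs by age, so the ranking around the median can shift. The mITTe set (SAP 3.2.1) requires only an extension dose and a Visit 7 score, and SAP 6.6 carries Visit 8 forward when the Visit 9 score is missing. A patient with no Visit 9 can therefore count in the extension primary endpoint while having no Visit 9 age, no defined Visit 7 ASIS and no ASIS subgroup.

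**The case against.** The strongest reply is the general age rule in section 10.1. The SAP never says in so many words that Visit 9 age applies at every visit, and a programmer who followed the general rule would use Visit 7 age for the Visit 7 ASIS. The bias would then vanish. The absence of any entry in section 7 also suggests that no departure from the protocol was meant, and the parenthesis in 6.6.3 could be read as describing the Visit 9 score only. This may well reflect the authors' intention. It does not rescue the text: the general rule does not name ASIS, whereas the specific definition names Visit 9 twice and offers no alternative. Two programmers could produce different versions of Table 14.2.73 from the same SAP.

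It is also true that the protocol does not spell out that age means age at scoring. That is an inference, but it fits the reported stability: with a fixed age, ASIS would rise with every point gained.

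The points on weight stand. Extension evaluations are exploratory, ASIS is descriptive with no test, and the 5-domain success endpoint does not use it. The protocol separately allows a before-and-after slope analysis from retrospective NPC-CSS data. The excess is small in older adults. Nobody has shown that a patient would actually change subgroup. The error cannot create a false claim of benefit.

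**Conclusion.** The definition is wrong as written. Read literally, the planned ASIS change equals (S9 − S7)/A9 and exceeds the own-age change by S7 × d/(A7 × A9). That is 2% to 14% of the Visit 7 ASIS over ages 45 down to 6, always in the direction of worsening. The excess is zero only for a Visit 7 score of 0, which is unlikely because asymptomatic patients are excluded from the study. The direction and the percentages need only the algebra and a one-year interval; the absolute values also rest on the assumed score of 20. Bias here means relative to ASIS with age at each visit; a falling score still gives a negative change under either rule. The consequences are confined to an exploratory descriptive measure and one baseline subgroup of the extension, so this should be corrected but does not threaten the parent-study result or the overall extension primary result.

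**What to change.** In SAP 6.6.3 and 10.1, define ASIS at a visit as the 15-domain NPC-CSS total at that visit divided by the patient's age on that visit's date. State the change as ASIS at Visit 9 minus ASIS at Visit 7, each with its own age. In 6.5.3, state that the Visit 7 split uses age at Visit 7. If Table 14.2.73 extends beyond Visit 9, extend the general age rule to those visits, since it names only Visits 7, 8 and 9.

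This agrees with the protocol definition and with the SAP's own age rule. The cost is a few lines of text and one programming change. No new data are needed: visit dates are recorded, and the birth-date imputation in 10.1 can stay. SAP 10.1 notes that full birth dates are not provided, so age levels carry some imputation error. The same imputed birth date serves every visit, so the age difference between visits depends only on the visit dates.

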10.2 Coding

Coding of adverse events, concomitant medication and medical history will be performed by the Data Management provider. Adverse events and medical history are coded with the MedDRA coding system, version 23.0 including COVID-19 items as released on 19 April 2020. Concomitant medication is coded according to the WHO drug code and the ATC class code, using WHO ATC/DDD Index 2019. Coding will be supplied as part of the data transfer.

10.3 Analysis software

The statistical analysis and reporting will be done using SAS® for Windows™ version 9.4. SAS tabular output (tables and listings) will be saved in RTF format. SAS graphs will be saved in PNG format. Both will be imported into PDF and/or Word® and supplied to the Medical Writer for use in the clinical study report. When the sponsor wants to receive the output before the study report, then a PDF document is supplied.

Furthermore, a number of excels will be provided to the client when providing the output. For the Parent phase this may concern the CI-CS Visit 2 to Visit 6 for each patient and the CI-S primary anchor data for each patient at each visit from the Parent Study, and the excels for creation of Forest plots of the Parent Study.

10.4 Presentation of tables, listings, graphs

All output will be generated as SAS tables, graphs and listings.

All tables and listings will be created such that they fit landscape pages. The tables for the end-of-text and listings for the appendix will be created using SAS, following the specifications according to the TLF template document that will be created separately.

For graphs, output will be as created as PNG plot. Graphs are preferably created using black, grey, and white color only, to facilitate black-and-white printing. Different line patterns and symbols will be used to differentiate between classification or treatment levels. If certain plots can only be visually improved by using colours, then this will be done using colors as

distinct as possible. Graphs will be created such (i.e. taking into account line thickness and font size) that they can be presented as two (2) per page in the clinical study report.

11 TABLES, LISTINGS, GRAPHS – PARENT STUDY

11.1 General

A detailed list of tables, graphs and listings is presented, if applicable, per report section in Sections 11.2, 11.3 and 11.4.

Template tables and listings as well as *example* plots (as received from client or extracted from a relevant paper, if available) will be used as a reference for creation of all output, and a separate document will be created for this. Table/graph/listing numbering will be followed, however, if the data give cause for combining or splitting tables or listings, the numbering may be adapted as necessary. In case there are no data available for a certain table/listing, an empty table will be created and 'No data available' will be stated.

11.2 In-text tables and graphs

Not applicable. Will be designed or extracted by the Medical Writer during creation of the Clinical Study Report, based on the tables and graphs created for Section 14 of the CSR.

11.3 End-of-text tables and graphs

Following ICH E3 guidelines, all tables and graphs mentioned here will be presented in Section 14 of the CSR, and tables will be prepared in the order and with section number as stated.

Table/graph number	Contents of table/graph
14.1 Demographic Data Summary figures and tables	
14.1.1-14.1.4	Demographics (ITT, mITT, PPS and SAF population)
14.1.5-14.1.7	Baseline characteristics (ITT, mITT and PPS population)
14.1.7	Disposition
14.1.8	Medical history
14.1.9	NPC specific history
14.1.10	Compliance
14.2 Efficacy Data Summary figures and Tables	
14.2.1	Result of t-test or Wilcoxon test on the primary endpoint (mITT and PPS), including sensitivity analysis (only mITT).
14.2.2	Frequency table of the CI-CS score Visit 4 vs Visit 2 minus the CI-CS score Visit 6 vs Visit 4, combined with the frequency table of the CI-CS score Visit 4 vs Visit 2 and separately, the CI-CS score Visit 6 vs Visit 4 (mITT and PPS population)

14.2.3	Descriptive statistics of the CI-CS score Visit 4 vs Visit 2 minus the CI-CS score Visit 6 vs Visit 4, combined with the descriptive statistics of the CI-CS score Visit 4 vs Visit 2 and separately, the CI-CS score Visit 6 vs Visit 4 (mITT and PPS population).
14.2.4	Bar chart of CI-CS score Visit 4 vs Visit 2 minus CI-CS score Visit 6 vs Visit 4 (mITT and PPS population)
14.2.5	Frequency table of the CI-CS score Visit 4 vs Visit 2 minus the CI-CS score Visit 6 vs Visit 4 according to subgroups, combined with the frequency table of the CI-CS score Visit 4 vs Visit 2 and separately, the CI-CS score Visit 6 vs Visit 4 according to subgroups (mITT population)
14.2.6	Descriptive statistics of the CI-CS score Visit 4 vs Visit 2 minus the CI-CS score Visit 6 vs Visit 4 according to subgroups, combined with the descriptive statistics of the CI-CS score Visit 4 vs Visit 2 and separately, the CI-CS score Visit 6 vs Visit 4 according to subgroups (mITT population)
14.2.7	Bar chart of CI-CS score Visit 4 vs Visit 2 and separately, CI-CS score Visit 6 vs Visit 4 (mITT and PPS population)
14.2.8	Pearson rank correlation coefficients (mITT population)
14.2.9	Bland-Altman plots (mITT population)
14.2.10	Result of t-test or Wilcoxon test on the key secondary endpoint 'Change in severity score based on averaged CI-S' (mITT and PPS population),
14.2.11	Frequency table of the change in severity score based on averaged CI-S scores between baseline and treatment minus the change between treatment and washout (mITT and PPS population)
14.2.12	Descriptive statistics of the change in severity score based on averaged CI-S scores between baseline and treatment minus the change between treatment and washout (mITT and PPS population)
14.2.13	Bar chart of change in severity score based on averaged CI-S scores between baseline and treatment minus the change between treatment and washout (mITT and PPS population)
14.2.14	Frequency table of the change in severity score based on averaged CI-S scores between baseline and treatment minus the change between treatment and washout according to subgroups (mITT population)
14.2.15	Descriptive statistics of change in severity score based on averaged CI-S scores between baseline and treatment minus the change between treatment and washout according to subgroups (mITT population)
14.2.16	Result of Wilcoxon test on the key secondary endpoint 'CI-CS score reclassified' (mITT and PPS)
14.2.17	Frequency table of the CI-CS score reclassified on a 3-point scale Visit 4 vs Visit 2 and separately, the reclassified CI-CS score Visit 6 vs Visit 4 (mITT and PPS population)

14.2.18	Descriptive statistics of the CI-CS score reclassified on a 3-point scale Visit 4 vs Visit 2 and separately, the reclassified CI-CS score Visit 6 vs Visit 4 (mITT and PPS population)
14.2.19	Bar chart of CI-CS score reclassified on a 3-point scale Visit 4 vs Visit 2 and separately, CI-CS score Visit 6 vs Visit 4 (mITT and PPS population)
14.2.20	Frequency table of the CI-CS score reclassified on a 3-point scale Visit 4 vs Visit 2 and separately, the reclassified CI-CS score Visit 6 vs Visit 4 according to subgroups (mITT population)
14.2.21	Descriptive statistics of the CI-CS score reclassified on a 3-point scale Visit 4 vs Visit 2 and separately, the reclassified CI-CS score Visit 6 vs Visit 4 according to subgroups (mITT population)
14.2.22	Frequency table of the CI-CS score for the non-primary anchor test Visit 4 vs Visit 2 and separately, the CI-CS score Visit 6 vs Visit 4 (mITT and PPS population)
14.2.23	Descriptive statistics of the CI-CS score for the non-primary anchor test Visit 4 vs Visit 2 and separately, the CI-CS score Visit 6 vs Visit 4 (mITT and PPS population)
14.2.24	Frequency table of the CI-CS score for the non-primary anchor test Visit 4 vs Visit 2 and separately, the CI-CS score Visit 6 vs Visit 4 according to subgroups (mITT population)
14.2.25	Descriptive statistics of the CI-CS score for the non-primary anchor test Visit 4 vs Visit 2 and separately, the CI-CS score Visit 6 vs Visit 4 according to subgroups (mITT population)
14.2.26	Result of t-test or Wilcoxon test on the change in SARA total score between Visit 2 and Visit 4, as well as Visit 4 and Visit 6 (mITT and PPS population)
14.2.27	Descriptive statistics of the SARA total score and 8 subscores at each visit (mITT and PPS population)
14.2.28	Mean or median plot versus time of the SARA total score (mITT and PPS population)
14.2.29	Stacked bar chart of the 8 SARA subscores at each visit (mITT and PPS population)
14.2.30	Spaghetti plot of SARA total score at each visit (mITT and PPS population)
14.2.31	Descriptive statistics of the SARA total score and 8 subscores at each visit according to subgroups (mITT population)
14.2.32	Result of t-test or Wilcoxon test on the change in SCAFI total score, and subscores 8MW_avg, 9HPT-D_avg and PATA_avg between Visit 2 and Visit 4, as well as Visit 4 and Visit 6 (mITT and PPS population)
14.2.33	Descriptive statistics of the SCAFI total score and subscores 8MW_avg, 9HPT-D_avg, 9HPT-ND_avg and PATA_avg at each visit (mITT and PPS population)

14.2.34	Mean or median plot of SCAFI total score versus time (mITT and PPS population)
14.2.35	Spaghetti plot of SCAFI total score versus time (mITT and PPS population)
14.2.36	Descriptive statistics of the SCAFI total score and subscores 8MW_avg, 9HPT-D_avg, 9HPT-ND_avg and PATA_avg at each visit according to subgroups (mITT population)
14.2.37	Frequency table of the EQ-5D-5L and EQ-5D-Y health status and 5 subdomains at each visit (mITT and PPS population)
14.2.38	Frequency table of the EQ-5D-5L and EQ-5D-Y health status and 5 subdomains at each visit according to subgroups (mITT population)
14.2.39	Descriptive statistics of the EQ-VAS for -5L and -Y combined at each visit (mITT and PPS population)
14.2.40	Mean or median plot of EQ-VAS versus time for -5L and -Y combined (mITT and PPS population)
14.2.41	Spaghetti plot of EQ-VAS versus time for -5L and -Y combined (mITT and PPS population)
14.2.42	Descriptive statistics of the EQ-VAS for -5L and -Y combined at each visit according to subgroups (mITT population)
14.2.43	Descriptive statistics on the change in mDRS composite score between Visit 2 and Visit 4, as well as Visit 4 and Visit 6 (mITT and PPS population)
14.2.44	Descriptive statistics of the mDRS composite score and 6 components at each visit (mITT and PPS population)
14.2.45	Mean or median plot versus time of the mDRS composite score (mITT and PPS population)
14.2.46	Spaghetti plot of the mDRS composite score versus time (mITT and PPS population)
14.2.47	Descriptive statistics of the mDRS composite score and 6 components at each visit according to subgroups (mITT population)
14.2.48	Frequency table of the 3 CGI-S scores (treating physician, caregiver and patient) at each visit (mITT and PPS population)
14.2.49	Descriptive statistics of the 3 CGI-S scores (treating physician, caregiver and patient) at each visit (mITT and PPS population)
14.2.50	Bar charts of the 3 CGI-S scores (treating physician, caregiver and patient) at each visit (mITT and PPS population)
14.2.51	Mean or median plot versus time of the 3 CGI-S scores (treating physician, caregiver and patient) (mITT and PPS population)
14.2.52	Spaghetti plot of the 3 CGI-S scores (treating physician, caregiver and patient) versus time (mITT and PPS population)

14.2.53	Frequency table of the 3 CGI-S scores (treating physician, caregiver and patient) at each visit according to subgroups (mITT population)
14.2.54	Descriptive statistics of the 3 CGI-S scores (treating physician, caregiver and patient) at each visit according to subgroups (mITT population)
14.2.55	Frequency table of the 3 CGI-C scores (treating physician, caregiver and patient) between Visit 2 vs Visit 4, and between Visit 4 and Visit 6 (mITT and PPS population)
14.2.56	Descriptive statistics of the 3 CGI-C scores (treating physician, caregiver and patient) between Visit 2 vs Visit 4, between Visit 4 and Visit 6, and Visit 4 vs Visit 2 minus the CI-CS score Visit 6 vs Visit 4 (mITT and PPS population).
14.2.57	Result of t-test or Wilcoxon test on the change of CGI-C score for treating physician Visit 4 vs Visit 2 minus Visit 6 vs Visit 4 (mITT and PPS population)
14.2.58	Result of t-test or Wilcoxon test on the change of CGI-C score for treating physician between Visit 2 and Visit 4, as well as Visit 4 and Visit 6 (mITT and PPS population)
14.2.59	Bar charts of the 3 CGI-C scores (treating physician, caregiver and patient) between Visit 2 vs Visit 4, and between Visit 4 and Visit 6 (mITT and PPS population)
14.2.60	Frequency table of the 3 CGI-C scores (treating physician, caregiver and patient) between Visit 2 vs Visit 4, and between Visit 4 and Visit 6 according to subgroups (mITT population)
14.2.61	Descriptive statistics of the 3 CGI-C scores (treating physician, caregiver and patient) between Visit 2 vs Visit 4, and between Visit 4 and Visit 6 according to subgroups (mITT population)
14.2.62	Forest plots
14.3 Safety Data Summary figures and tables – 14.3.1 Displays of Adverse Events	
14.3.1.1	Overview adverse events
14.3.1.2	Treatment emergent adverse events
14.3.1.3	Treatment emergent adverse events by severity grade
14.3.1.4	Treatment emergent adverse events by relationship
14.3.1.5	Treatment emergent adverse events leading to premature discontinuation
14.3.1.6	Treatment emergent adverse events by treatment cycle
14.3.1.7	Treatment emergent adverse events by severity grade by treatment cycle
14.3.1.8	Treatment emergent adverse events by relationship by treatment cycle
14.3.1.9	Treatment emergent adverse events leading to premature discontinuation by treatment cycle

14.3 Safety Data Summary figures and tables – 14.3.2 Listings of Deaths, Other Serious and Significant Adverse Events	
14.3.2.1	SAEs
14.3.2.2	Deaths
14.3 Safety Data Summary figures and tables – 14.3.4 Abnormal Laboratory Value Listing (each patient)	
14.3.4.1	Out of range clinical laboratory
14.3.4.2	Clinical laboratory – haematology
14.3.4.3	Clinical laboratory – clinical chemistry
14.3.4.4	Clinical laboratory – urinalysis
14.3.5	Vital signs
14.3.6	ECG
14.3.7	Prior and concomitant medication and therapies

